### **8.3.3 Additional Testing**

Participants with clinical suspicion of retinal abnormalities (ie, RPED, serous detachment of the retina, RVO, photopsia, metamorphopsia, impairment of visual acuity), must complete at least one of the following additional assessments:

- For non-vascular abnormalities: optical coherence tomography (OCT) of the macula (spectral domain OCT recommended)
- For vascular abnormalities: fluorescein angiography of the central 30 degrees.
- Images/results of the ophthalmic examinations (at a minimum, OCT and/or fluorescein angiography) should be sent to the study site and be maintained in the participant's source document file. These images/results may be requested to be sent to the Sponsor or designee.

### 8.3.4 Vital Signs

The investigator or qualified designee will take vital signs at the Screening Visit, prior to the administration of each dose of study intervention and at the EoT Visit as specified in the SoA (Section 1.3). Vital signs include temperature, pulse, respiratory rate, and blood pressure. Height will be measured at the Screening Visit only.

Blood pressure and pulse measurements should be performed with a completely automated device. Manual techniques will be used only if an automated device is not available. The participant should be in a semi-recumbent or supine position for at least 10 minutes prior to having the measurement performed. The correct size of the blood pressure cuff and correct positioning of the participant's arm are essential to the accuracy of the blood pressure measurement.

### 8.3.5 Electrocardiograms

A standard 12-lead ECG will be performed using local standard procedures. The timing of ECGs is specified in the SoA (Section 1.3). Clinically significant abnormal findings should be recorded as medical history. Additional ECGs may be performed as clinically necessary.

- A standard 12-lead ECG will be performed using local standard procedure.
- The ECG measurement performed at the Screening Visit will be used to determine eligibility.
- The ECG measurement at any time point should be used for AE grading and recommended dose modifications.
- When an ECG is to be performed at the same time point as a blood collection, the ECG is to be performed first.
- ECG will be performed predose at every visit starting at C2D1.

**Screening:** Triplicate 12-lead ECGs will be obtained at the Screening Visit only.

Three individual ECG tracings should be obtained as closely as possible in succession, but no more than 2 minutes apart. The full set of triplicates should be completed in less than 4 minutes. Refer to Section 5.2 (Exclusion Criterion 7 for QTcF withdrawal criteria).

### 8.3.6 Echocardiogram/Multigated Acquisition Scan

Cardiac ejection fraction will be assessed by transthoracic ECHO or MUGA scans at the time points specified in the SoA (Section 1.3). The same method should be used throughout the study. Participants who develop signs/symptoms of CHF at any point during the study are required to have an evaluation of LVEF measurement by ECHO or MUGA.

### 8.3.7 Clinical Safety Laboratory Assessments

- Refer to Appendix 2 for the list of clinical laboratory tests to be performed and to the SoA for the timing and frequency.
- The investigator or medically qualified designee (consistent with local requirements) must review the laboratory report, document this review, and record any clinically relevant changes occurring during the study in the AE section of the case report form (CRF). The laboratory reports must be filed with the source documents. Clinically significant abnormal laboratory findings are those which are not associated with the underlying disease, unless judged by the investigator to be more severe than expected for the participant's condition.
- All protocol-required laboratory assessments, as defined in Appendix 2, must be conducted in accordance with the laboratory manual and the SoA.
- If laboratory values from nonprotocol specified laboratory assessments performed at the institution's local laboratory require a change in study participant management or are considered clinically significant by the investigator (eg, SAE or AE or dose modification), then the results must be recorded in the appropriate CRF (eg, SLAB).
- For any laboratory tests with values considered clinically significantly abnormal during participation in the study or within 30 days after the last dose of study intervention, every attempt should be made to perform repeat assessments until the values return to normal or baseline or if a new baseline is established as determined by the investigator.

### 8.4 Adverse Events (AEs), Serious Adverse Events (SAEs), and Other Reportable Safety Events

The definitions of an AE or SAE, as well as the method of recording, evaluating, and assessing causality of AE and SAE and the procedures for completing and transmitting AE, SAE, and other reportable safety event reports can be found in Appendix 4.

Progression of the cancer under study is not considered an AE unless it results in hospitalization or death as described in Section 8.4.6 and Appendix 3.

Adverse events, SAEs, and other reportable safety events will be reported by the participant (or, when appropriate, by a caregiver, surrogate, or the participant's legally authorized representative).

The investigator and any designees are responsible for detecting, documenting, and reporting events that meet the definition of an AE or SAE as well as other reportable safety events. Investigators remain responsible for following up AE, SAEs, and other reportable safety events for outcome according to Section 8.4.3.

The investigator, who is a qualified physician, will assess events that meet the definition of an AE or SAE as well as other reportable safety events with respect to seriousness, intensity/toxicity and causality.

#### **8.4.1 Time Period and Frequency for Collecting AE, SAE, and Other Reportable Safety Event Information**

All AEs, SAEs, and other reportable safety events that occur after the consent form is signed but before treatment allocation/randomization must be reported by the investigator if the participant is receiving placebo run-in or other run-in treatment, if the event cause the participant to be excluded from the study, or is the result of a protocol-specified intervention, including but not limited to washout or discontinuation of usual therapy, diet, or a procedure.

- All AEs from the time of treatment allocation/randomization through 30 days following cessation of study intervention must be reported by the investigator.
- All AEs meeting serious criteria, from the time of treatment allocation/randomization through 90 days following cessation of study intervention or 30 days following cessation of study intervention if the participant initiates new anticancer therapy, whichever is earlier, must be reported by the investigator.
- All pregnancies and exposure during breastfeeding, from the time of treatment allocation/randomization through 120 days following cessation of study intervention, or 30 days following cessation of study intervention if the participant initiates new anticancer therapy must be reported by the investigator.
- Additionally, any SAE brought to the attention of an investigator at any time outside of the time period specified above must be reported immediately to the Sponsor if the event is considered drug-related.

Investigators are not obligated to actively seek AE or SAE or other reportable safety events in former study participants. However, if the investigator learns of any SAE, including a death, at any time after a participant has been discharged from the study, and he/she considers the event to be reasonably related to the study intervention or study participation, the investigator must promptly notify the Sponsor.

All initial and follow-up AEs, SAEs, and other reportable safety events will be recorded and reported to the Sponsor or designee within the time frames as indicated in [Table 9](#).

Table 9 Reporting Time Periods and Time Frames for Adverse Events and Other Reportable Safety Events

Type of Event	Reporting Time Period: Consent to Randomization/ Allocation	Reporting Time Period: Randomization/ Allocation through Protocol-Specified Follow-up Period	Reporting Time Period: After the Protocol Specified Follow-up Period	Timeframe to Report Event and Follow-up Information to SPONSOR:
Non-Serious Adverse Event (NSAE)	Report if: - due to protocol-specified intervention - causes exclusion - participant is receiving placebo run-in or other run-in treatment	Report all	Not required	Per data entry guidelines
Serious Adverse Event (SAE) including Cancer and Overdose	Report if: - due to protocol-specified intervention - causes exclusion - participant is receiving placebo run-in or other run-in treatment	Report all	Report if: - drug/vaccine related. (Follow ongoing to outcome)	Within 24 hours of learning of event
Pregnancy/Lactation Exposure	Report if: - due to intervention - causes exclusion	Report all	Previously reported – Follow to completion/termination; report outcome	Within 24 hours of learning of event
Event of Clinical Interest (ECI) (require regulatory reporting)	Report if: - due to intervention - causes exclusion	Report - Potential Drug-induced liver injury (DILI) - Require regulatory reporting	Not required	Within 24 hours of learning of event
ECI (Do not require regulatory reporting)	Report if: - due to intervention - causes exclusion	Report - non-DILI ECIs and those not requiring regulatory reporting	Not required	Within 5 calendar days of learning of event

#### **8.4.2 Method of Detecting AEs, SAEs, and Other Reportable Safety Events**

Care will be taken not to introduce bias when detecting AEs and/or SAEs and other reportable safety events. Open-ended and nonleading verbal questioning of the participant is the preferred method to inquire about AE occurrence.

#### **8.4.3 Follow-up of AE, SAE, and Other Reportable Safety Event Information**

After the initial AE/SAE report, the investigator is required to proactively follow each participant at subsequent visits/contacts. All AE, SAE, and other reportable safety events including pregnancy and exposure during breastfeeding, events of clinical interest (ECI), cancer, and overdose will be followed until resolution, stabilization, until the event is otherwise explained, or the participant is lost to follow-up (as defined in Section 7.3). In addition, the investigator will make every attempt to follow all nonserious AEs that occur in study participants for outcome. Further information on follow-up procedures is given in Appendix 3.

#### **8.4.4 Regulatory Reporting Requirements for SAE**

Prompt notification (within 24 hours) by the investigator to the Sponsor of SAE is essential so that legal obligations and ethical responsibilities towards the safety of participants and the safety of a study intervention under clinical investigation are met.

The Sponsor has a legal responsibility to notify both the local regulatory authority and other regulatory agencies about the safety of a study intervention under clinical investigation. All AEs will be reported to regulatory authorities, IRB/IECs, and investigators in accordance with all applicable global laws and regulations (ie, per ICH Topic E6 (R2) Guidelines for Good Clinical Practice [GCP]).

Investigator safety reports must be prepared for suspected unexpected serious adverse reactions (SUSARs) according to local regulatory requirements and Sponsor policy and forwarded to investigators as necessary.

An investigator who receives an investigator safety report describing an SAE or other specific safety information (eg, summary or listing of SAE) from the Sponsor will file it along with the IB and will notify the IRB/IEC, if appropriate according to local requirements.

#### **8.4.5 Pregnancy and Exposure During Breastfeeding**

Although pregnancy and infant exposure during breastfeeding are not considered AEs, any pregnancy or infant exposure during breastfeeding in a participant (spontaneously reported to the investigator or their designee) that occurs during the study are reportable to the Sponsor.

All reported pregnancies must be followed to the completion/termination of the pregnancy. Pregnancy outcomes of spontaneous abortion, missed abortion, benign hydatidiform mole, blighted ovum, fetal death, intrauterine death, miscarriage, and stillbirth must be reported as

serious events (Important Medical Events). If the pregnancy continues to term, the outcome (health of infant) must also be reported.

#### **8.4.6 Disease-related Events and/or Disease-related Outcomes Not Qualifying as AEs or SAEs**

Progression of the cancer under study is not considered a reportable event unless it results in hospitalization or death.

#### **8.4.7 Events of Clinical Interest (ECIs)**

Selected nonserious and SAEs are also known as ECIs and must be reported to the Sponsor.

Events of clinical interest for this study include:

- An overdose of Sponsor's product, as defined in Section 8.5, that is not associated with clinical symptoms or abnormal laboratory results.
- An elevated AST or ALT lab value that is greater than or equal to 3X the upper limit of normal and an elevated total bilirubin lab value that is greater than or equal to 2X the upper limit of normal and, at the same time, an alkaline phosphatase lab value that is less than 2X the upper limit of normal, as determined by way of protocol-specified laboratory testing or unscheduled laboratory testing.\*

\*Note: These criteria are based upon available regulatory guidance documents. The purpose of the criteria is to specify a threshold of abnormal hepatic tests that must trigger an additional evaluation for an underlying etiology. The study site guidance for assessment and follow up of these criteria can be found in the Investigator Study File Binder (or equivalent).

### **8.5 Treatment of Overdose**

For purposes of this study, an overdose will be defined as any dose exceeding the prescribed dose for MK-8353 and/or selumetinib by  $\geq 20\%$  of the indicated single dose. No specific information is available on the treatment of overdose of MK-8353 and/or selumetinib. In the event of overdose, MK-8353 and selumetinib should be discontinued and the participant should be observed closely for signs of toxicity. Appropriate supportive treatment should be provided if clinically indicated.

### **8.6 Pharmacokinetics**

#### **8.6.1 Blood Collection for Plasma**

Sample collection, storage, and shipment instructions for PK samples will be provided in the operations/laboratory manual for both MK-8353 and selumetinib.

Pharmacokinetic samples should be drawn according to the PK collection schedule for all participants. The exact time of sample collection and time of administration of MK-8353 and selumetinib will be recorded.

#### **8.6.1.1 MK-8353 Blood Collection for Plasma**

Blood samples for determination of plasma concentrations of MK-8353. Plasma samples for MK-8353 will be obtained from consenting participants. Serial plasma samples for PK analysis of MK-8353 will be collected C1D1 and C1D4 at time 0 (within 24 hours prior to pre-dose for C1D1 or within -10 minutes prior to pre-dose for C1D4 trough sample), post-dose at 1(± 10 minutes), 2 (± 10 minutes), 4(± 10 minutes), 6 (± 10 minutes), and 1 sample any time between 8 and 12 hours (prior to PM dosing for BID regimen). Additional samples will be collected at pre-dose/trough (within -10 minutes prior to pre-dose), hours 1 (± 10 minutes), and hours 4 (± 10 minutes) at C2D1, C2D4, C5D1, C5D4. The exact time of sample collection and time of administration of MK-8353 will be recorded.

#### **8.6.1.2 Selumetinib Blood Collection for Plasma**

Blood samples for determination of plasma concentrations of selumetinib and N-desmethyl selumetinib. Other metabolites (eg, selumetinib amide) may also be determined. Plasma samples for selumetinib and N-desmethyl selumetinib will be obtained from consenting participants. Serial plasma samples for PK analysis of selumetinib and N-desmethyl selumetinib will be collected C1D1 and C1D4 at time 0 (within 24 hours prior to pre-dose for C1D1 and within -10 minutes prior to pre-dose for C1D4 trough sample), post-dose at 1(± 10 minutes), 2 (± 10 minutes), 4 (± 10 minutes), 6 (± 10 minutes), and 1 sample any time between 8 and 12 hours (prior to PM dosing for BID regimen). Additional samples will be collected at pre-dose/trough (within -10 minutes prior to pre-dose), hours 1 (± 10 minutes), and hours 4 (± 10 minutes) at C2D1, C2D4, C5D1, C5D4. The exact time of sample collection and time of administration of selumetinib will be recorded.

Based on observed toxicity and severity of toxicity, we may pause the study and analyze PK to assess if there is a need to modify the dose/dosing schedule (eg, lower the dose; change from BID to QD).

### **8.7 Pharmacodynamics**

Sample collection, storage, and shipment instructions for pharmacodynamic samples will be provided in operations/laboratory manual.

### **8.8 Future Biomedical Research Sample Collection**

If the participant signs the future biomedical research consent, the following specimens will be obtained as part of future biomedical research:

- Leftover from specimens listed in Section 8.10, Biomarkers.

## 8.9 Planned Genetic Analysis Sample Collection

The planned genetic analysis sample should be drawn for planned analysis of the association between genetic variants in DNA and drug response. This sample will not be collected at the site if there is either a local law or regulation prohibiting collection, or if the IRB/IEC does not approve the collection of the sample for these purposes. If the sample is collected, leftover extracted DNA will be stored for future biomedical research if the participant signs the future biomedical research consent. If the planned genetic analysis is not approved, but future biomedical research is approved and consent is given, this sample will be collected for the purpose of future biomedical research.

## 8.10 Biomarkers

To identify novel biomarkers, the following biospecimens to support exploratory analyses of cellular components (eg, protein, RNA, DNA, metabolites) and other circulating molecules will be collected from all participants as specified in the SoA:

- Blood for Genetic Analysis
- Blood for ctDNA
- Blood for RNA Analyses
- Blood for Plasma Biomarker Analyses
- Blood for Serum Biomarker Analyses
- Blood for pERK
- Archival or Newly Obtained Tumor Tissue collection
- On-treatment Tumor Biopsy (Optional)

Sample collection, storage, and shipment instructions for the exploratory biomarker specimens will be provided in the Procedures Manual.

### *Exploratory FDG-PET:*

Exploratory imaging will be used as a biomarker of the study drugs. FDG-PET scans will be obtained from participants at the MTD levels only as specified in the SoA. Details for the collection and storage scans will be provided in the operations/laboratory manual.

## 8.11 Visit Requirements

Visit requirements are outlined in Section 1.3. Specific procedure-related details are provided in Section 8.

### **8.11.1 Screening**

Written consent must be obtained prior to performing any protocol specific procedure. Results of a test performed prior to the participant signing consent as part of routine management are acceptable in lieu of a screening test if performed within the specified time frame. Screening procedures are to be completed within 28 days prior to the first dose of study intervention except for the following:

- Laboratory tests are to be performed within 10 days prior to the first dose of trial treatment. An exception is hepatitis testing, which may be done up to 28 days prior to the first dose of trial treatment.
- Evaluation of ECOG is to be performed within 7 days prior to the first dose of trial treatment.
- For women of reproductive potential, a urine or serum pregnancy test will be performed within 72 hours prior to the first dose of trial treatment. If urine pregnancy results cannot be confirmed as negative, a serum pregnancy test will be required (performed by the local study site laboratory).
- Archival tumor sample collection is not required to be obtained within 28 days prior to the first dose of trial treatment. Newly obtained tumor tissue may be obtained within 90 days of treatment initiation.

### **8.11.2 Treatment Period**

Visit requirements are outlined in the SoA (Section 1.3). Specific procedure-related details are provided above in Section 8 – Study Assessments and Procedures.

### **8.11.3 Discontinued Participants Continuing to be Monitored in the Study**

The Discontinuation Visit should occur at the time study treatment is discontinued for any reason. If the Discontinuation Visit occurs 30 days from the last dose of study treatment, at the time of the mandatory Safety Follow-up Visit, the Discontinuation Visit procedures and any additional Safety Follow-up procedures should be performed. For participants who discontinue study treatment without documented disease progression, every effort should be made to continue monitoring their disease status by radiologic imaging in post-treatment follow up visits. Imaging will not be collected during Survival Follow-up Visit(s). Visit requirements are outlined in the SoA (Section 1.3). Additional details regarding participant withdrawal and discontinuation are presented in Section 8.1.9 –Discontinuation and Withdrawal. Additional details regarding Post-treatment Follow-up imaging visits are represented in Section 8.2.1.3 – End of Treatment and Follow-up Imaging.

### **8.11.4 Post-treatment**

Participants will be required to return to clinic approximately 30 days after the last dose of study intervention for the post-treatment Safety Follow-up Visit. If a participant initiates a

new anticancer therapy within 30 days after the last dose of study treatment, the Post-treatment Safety Follow-up Visit should occur before the first dose of the new therapy.

After treatment discontinuation, each participant will be followed for up to 30 days for AE monitoring. Participants will be monitored for SAEs for 90 days after treatment discontinuation, 30 days if the participant initiates new anticancer therapy less than 30 days after study treatment discontinuation, or until the day new anticancer therapy is initiated if between 30 days and 90 days after study treatment discontinuation. Participants with an ongoing AE of Grade >1 at the time of treatment discontinuation will be followed until resolution of the AE to Grade 0 to 1, until considered stable by the treating physician, or until beginning a new anticancer therapy, whichever occurs first.

For participants who discontinue study treatment without documented disease progression, every effort should be made to continue monitoring disease status by radiologic tumor until the start of a new anticancer treatment, documented disease progression, pregnancy, death, withdrawal of consent, or the end of the study, whichever occurs first. The timing for these assessments should continue the same imaging schedule from the treatment phase (9 weeks  $\pm$  7 days in the first 12 months, or 12 weeks  $\pm$  14 days beyond 12 months – see Section 8.2.1.2 Tumor Imaging During the Study); Imaging should occur at any time where there is clinical suspicion of progression.

After confirmed disease progression, each subject will be contacted by telephone approximately every 12 weeks (84  $\pm$  7 days) for survival until withdrawal of consent to participate in the study, becoming lost to follow-up, death, or end of the study, whichever occurs first as shown in the SoA (Section 1.3).

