### 1.3.2 Dose Escalation: End of Treatment and Post-Treatment

Study Period: Treatment Cycle (C) / Visit:	End of Treatment (EoT) Discontinuation	Post-treatment			Notes
		Safety Follow-up	Follow-up Visits	Survival Follow-up	
Collection Timepoint: (Study Day [D])	At time of Treatment Discontinuation	30 days Post-last dose	Every 9 or 12 weeks Post-discontinuation	Every 12 weeks Post-last dose	
Scheduling Window (Days):	+7	+14	±7	±14	
Administrative Procedures					
Prior and Concomitant Medication Review	X	X			
Efficacy Assessments					
Tumor Imaging	X		X		In participants who discontinue study therapy without documented PD, tumor imaging should continue in Post-treatment Follow-up Visits, following the same imaging schedule from the treatment phase; and as clinically indicated.
Clinical Procedures/Assessments					
Review Adverse Events	X	X	X		Follow-up Visits: AEs will be collected when participant is in the clinic for tumor imaging assessment.
Full Physical Examination	X				
Full Ophthalmic Examination	X	X			Performed at the EoT. An ophthalmic examination at the Safety Follow-up Visit is only required if there was a clinically significant abnormality noted at EoT
Weight and Vital Signs	X				Vital signs: temperature, pulse, respiratory rate, and blood pressure
12-Lead Electrocardiogram	X	X			
Echocardiogram/ MUGA scan (Q12W)	X				
ECOG Performance Scale	X	X			
Post-study Anticancer Therapy Status			X	X	
Survival Status	X	X	X	X	All participants will be followed up for survival every 12 weeks (± 14 days) after discontinuation (unless consent is withdrawn). In addition, upon Sponsor request, participants may be contacted for survival status at any time during the study.

Study Period:	End of Treatment (EoT)	Post-treatment			Notes
Treatment Cycle (C) / Visit:	Discontinuation	Safety Follow-up	Follow-up Visits	Survival Follow-up	
Collection Timepoint: (Study Day [D])	At time of Treatment Discontinuation	30 days Post-last dose	Every 9 or 12 weeks Post-discontinuation	Every 12 weeks Post-last dose	
Scheduling Window (Days):	+7	+14	±7	±14	
LOCAL Laboratory Assessments					
CBC with Differential	X	X			
Chemistry Panel	X	X			Specific to creatinine: Cystatin C could be evaluated if creatinine is abnormal. Cystatin C may be conducted by central vendor only if analysis was not available from local study site laboratory.
Urinalysis	X	X			
Serum Tumor Marker	X	X			Collected as appropriate for tumor type.
CENTRAL Laboratory Assessments					

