## 6.6.4 Guidelines for Dose Modification Due to Adverse Events

### 6.6.4.1 Dose Modification for MK-8353 and Selumetinib

Adverse events (both nonserious and serious) associated with MK-8353 and selumetinib exposure may occur shortly after the first dose or several months after the last dose of treatment.

The CTCAE v4.0 must be used to grade the severity of AEs for individual participants. The investigator may attribute each toxicity event to MK-8353 alone, to selumetinib alone, or to the combination, but modification of the doses of both drugs must be followed according to [Table 7](#). Examples of dose reduction are as follows:

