### **8.2.1.3 End of Treatment and Follow-up Imaging**

For participants who discontinue study intervention, tumor imaging should be performed at the time of intervention discontinuation ( $\pm 4$  week window). If previous imaging was obtained within 4 weeks prior to the date of discontinuation, then imaging at intervention discontinuation is not mandatory. For participants who discontinue study treatment due to documented disease progression, this is the final required tumor imaging.

For participants who discontinue study treatment without documented disease progression, every effort should be made to continue monitoring disease status by radiologic tumor until the start of a new anticancer treatment, documented disease progression, pregnancy, death, withdrawal of consent, or the end of the study, whichever occurs first. The timing for these assessments should continue the same imaging schedule from the treatment phase (9 weeks  $\pm 7$  days in the first 12 months, or 12 weeks  $\pm 14$  days beyond 12 months – see Section 8.2.1.2); Imaging should occur at any time where there is clinical suspicion of PD.

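### The 90-day SAE period has no scheduled SAE question after Day 30-44 for participants who stop for progression, so new late nonfatal SAEs are detected only passively

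*Combined protocol and SAP*

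**What the plan says.** **The commitment.** Section 8.11.4 promises: "Participants will be monitored for SAEs for 90 days after treatment discontinuation". Section 8.4.1 makes SAEs reportable "through 90 days following cessation of study intervention or 30 days following cessation of study intervention if the participant initiates new anticancer therapy", whichever comes first.

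**The schedule.** In the SoA (Section 1.3.2) the adverse-event review row is marked at End of Treatment, Safety Follow-up and the imaging Follow-up Visits. It is blank under Survival Follow-up. Safety Follow-up is set at "30 days Post-last dose" with a +14-day window. For the imaging visits the note reads: "AEs will be collected when participant is in the clinic for tumor imaging assessment".

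**Who has imaging visits.** The SoA continues them for participants who stop without documented progression. For the others, Section 8.2.1.3 says: "For participants who discontinue study treatment due to documented disease progression, this is the final required tumor imaging".

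**What remains after progression.** Under Section 8.11.4, "each subject will be contacted by telephone approximately every 12 weeks", and the stated purpose is survival. The SoA marks only survival status and post-study anticancer therapy at that contact.

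**The concern.** A 90-day period works only if someone asks about events during it or at its end. The plan has such a contact for participants who keep attending for imaging. For those who stop because of progression it has none after the Safety Follow-up Visit.

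AEs are a primary endpoint (Section 3) and are summarised by counts and frequencies per dose level (Section 9.6.2). Section 6.6.4.1 itself says that drug-associated events "may occur shortly after the first dose or several months after the last dose of treatment". Deaths will come to light through survival status. A hospitalisation or other new nonfatal SAE on, say, Day 60 in a participant who has progressed depends on the site hearing of it some other way. A low late-SAE count at a dose level could then mean that few events occurred or that few were asked about, and which it means depends partly on why participants stopped.

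**Working it through.** The 90 days is a design choice, so the plan has no calculated figure to reproduce. The check is calendar arithmetic, with Day 0 taken as both last dose and discontinuation.

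**Inputs**
- SAE period: 90 days (8.11.4, 8.4.1).
- Safety Follow-up: Day 30, +14 (SoA 1.3.2), so Day 30 to 44.
- First survival contact: 84 ±14 days in SoA 1.3.2, so Day 70 to 98; 84 ±7 days in 8.11.4, so Day 77 to 91.
- Imaging interval: 63 days for the first 12 months, 84 days after that (8.2.1.2).

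**Step 1: stopped for progression, no new therapy.** Uncovered days = 90 − day of last AE review.
- 90 − 30 = 60 days (60/90 = 67%)
- 90 − 44 = 46 days (46/90 = 51%)

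**Step 2: stopped without progression.** The documents do not say when in the imaging cycle participants stop. I assume that the stop day is uniform within the interval *T* and ignore scan windows. With the Safety Follow-up Visit on day *L*:
- Share with a later AE review by Day 90 = (90 − L)/T.
- Mean last day asked = [(90 − T)(T + 90)/2 + (L − 90 + T)L + (T − L)(T + L)/2]/T.

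For T = 63 and L = 30 the mean is (27 × 76.5 + 3 × 30 + 33 × 46.5)/63 = 3690/63 = 58.6.

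| T | L | Share reviewed again by Day 90 | Mean last day asked | Mean days short of Day 90 | Mean days gained over a progressor |
|---|---|---|---|---|---|
| 63 | 30 | 60/63 = 95% | 58.6 | 31.4 | 28.6 |
| 63 | 44 | 46/63 = 73% | 60.8 | 29.2 | 16.8 |
| 84 | 30 | 60/84 = 71% | 51.4 | 38.6 | 21.4 |
| 84 | 44 | 46/84 = 55% | 56.6 | 33.4 | 12.6 |

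The table credits only visits up to Day 90. A later imaging visit might recover an event from inside the period by recall, but the documents do not say that it looks back. Crediting recall would widen the difference between groups.

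**Step 3: would the existing survival call close the gap if it carried an SAE question?** Not without a rule on its timing.
- Earliest call under the SoA: Day 70, leaving 90 − 70 = 20 days.
- Earliest call under 8.11.4: Day 77, leaving 90 − 77 = 13 days.
- A call on Day 90 or later that asks back to the last review leaves 0 days. The SoA window allows Day 90 to 98; the 8.11.4 window allows only Day 90 to 91.

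**The case against.** The strongest reply is that other provisions already cover the period. Section 8.4.1 and Table 9 make SAE reporting mandatory throughout it, and Section 8.4 makes the investigator responsible for detecting events. Section 8.4.3 requires proactive follow-up at later visits and contacts once an event has been reported, and a survival call is such a contact. Section 8.11.4 follows AEs above Grade 1 that are ongoing at discontinuation. A reader might infer from the blank SoA cell that late SAEs are found only by chance. These duties show that this is too strong: detection is passive, not random.

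The duties still do not close the gap. Reporting presupposes detection. Section 8.4 relies on the participant or a caregiver to report events, and Section 8.4.2 prefers open-ended questioning, which needs a contact. The proactive-follow-up and Grade >1 rules mainly concern events already known. None of them schedules a question about a new event.

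Three further points reduce the size of the gap.
- Table 8 calls for a repeat scan at 4 to 8 weeks in clinically stable participants with first radiologic progression, and survival calls under 8.11.4 start after *confirmed* progression. Someone who stops at first progression may therefore attend one more imaging visit. If it fell 56 days after the last dose and AEs were reviewed there, 90 − 56 = 34 days would remain. Section 8.2.1.3 points the other way, so it cannot be said that every such participant has no further visit, nor that any has one.
- New anticancer therapy closes the SAE period early and shortens or removes the gap for those who start it. The documents give no rate.
- Collection detail is partly left to data entry guidelines, which are not in these documents.

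**Conclusion.** The gap is real and limited. For a participant who stops for documented progression, starts no new anticancer therapy and has no confirmatory scan, 46 to 60 days of the SAE period carry no scheduled SAE question. How many participants this describes cannot be derived from the documents.

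A reader might take 51% to 67% as the size of a bias between participants who stop for different reasons. It is not: it is the progressors' own shortfall. Under the Step 2 assumptions, participants who stop without progression are also last asked 29 to 39 days before Day 90 on average. The average difference between the groups is about 13 to 29 days.

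A reader might also infer that the MTD or RP2D is distorted. The documents do not support that. DLTs are observed in Cycle 1 (Section 6.6.2, unless that window is modified), and the mTPI rules and the isotonic estimates use DLTs only. Late SAEs could enter through the review of all data before the RP2D is chosen (Section 4.1), where their influence is at most small. Nothing in the documents shows that reasons for stopping differ between combinations.

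What remains is incomplete and somewhat uneven late-SAE counts in the descriptive per-dose summaries of a primary endpoint. An absence of late SAEs among participants who progressed cannot be read as an absence of events. That justifies a correction, given how little it costs.

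**What to change.** 1. In SoA 1.3.2, mark an SAE-only adverse-event review at the first Survival Follow-up contact for every participant whose SAE period is still open, whatever the reason for stopping. Time that contact at or after Day 90.
2. State in Section 8.11.4 that SAEs since the last AE review are asked for at this call.
3. Reconcile the survival-call window (±7 days in 8.11.4, ±14 days in the SoA) and its start point (confirmed progression in 8.11.4, discontinuation or last dose in the SoA). Without this, part of the Day 90 to 98 slot breaches 8.11.4, and an untimed call can leave the 13 to 20 days shown above.
4. Give the SAE period one closing rule, so that a site can tell whether it is still open. When new therapy starts between Day 30 and Day 90, Section 8.4.1 ends collection at 30 days, whereas Section 8.11.4 continues "until the day new anticancer therapy is initiated if between 30 days and 90 days after study treatment discontinuation".

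The cost is one question in a call that is already scheduled, the wording changes, and a few more SAE forms, many of them probably disease-related. No visit is added and no treatment rule changes.
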